12.2.2 Primary endpoint

Main criterion for evaluation in the trial will be:

- Scores determined by the Local Tonsillitis Manifestations Scale refined by McIsaac's scale. Scores will be dichotomized to decide for two categories (therapy effective/therapy ineffective).
Scores will be evaluated by treatment and time point, i.e. per visit
- Need for an antibacterial therapy, i.e. number of patients per treatment.

12.2.3 Secondary endpoints

- Scores/Intensity of each underlying disease symptom assessed by the Local Tonsillitis Manifestations Scale by treatment and time point, i.e. per visit
- Axillary temperature per treatment and measurement time point
- Patient's self-assessments on VAS per treatment and measurement time point
- Self-assessment of the symptoms by the patient.

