
Sample size calculation
	
Justification of the number of subjects
 
This trial is parallel, two-group, with the same size groups.
 
The planned test power is 80% (the probability of making a second kind error is 0.2), the two-way probability of making a type 1 error is 0.05. The sample size was estimated by the main variable of the clinical trial.
 
Thus, this trial was a comparative for superior efficiency.
 
When proving superior therapeutic efficacy, the following statistical hypotheses are tested:
 
H0: e £ d versus On: e > d, where d is the limit of greater efficiency — the marginal value of clinically important differences, at which it can be considered that the tested drug exceeds its effectiveness by control (in this study it was taken equal to 15%); e - estimated (observed) differences between groups in therapeutic efficacy.
 
Given that the main variable is dichotomous, the size of each group can be estimated using the following expressions:
 
n control = k · n main
 $n_{main} = \frac{(z_{\alpha} + z_{\beta})^2}{(\varepsilon - \delta)^2} \cdot \left[\frac{p_{control} \cdot (1 - p_{control})}{k} + p_{main} \cdot (1 - p_{main}) \right]$ 
where: z_{α} and z_{β} —the corresponding percentage points of the standard normal distribution; d - the minimum acceptable value of clinically important differences; e - presumed (observable) differences between groups on therapeutic efficacy (the difference between the shares of positive results in groups); pcontrol and p main —shares of positive results in the

main and control groups, respectively; k - coefficient for unequal number of patients in groups (control is greater than the main); n_{main} и $n_{control}$ - the planned number of patients in the main and control groups, respectively; α is the boundary value of the error of the 1st kind (level of significance); β - is the boundary value of the error of the second kind.

In the planned study, it was assumed that the number of patients in the main and control groups was the same ($k = 1$), the significance level was $\alpha = 0.05$ (two-sided); the boundary value of the error of the second kind is $\beta = 0.2$ (which makes it possible to achieve a research power of 80%). Baseline data and the results of calculations using the above formula are given in Table. 1.

Table 1 - Baseline and Sample Size Estimation Results

Statistical indicator	Value of the indicator
Multiplicity factor k	1

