Boundary probability error of the first kind α	0,025
The probability of an error of the second kind β	0,2
The percentage point S.N.R. for α	1,96
The percentage point S.N.R. for β	0,84
The observed frequency of the positive effect for the control group $p_{control}$	0,75
Estimated value of the positive effect for the main group p_{main}	0,90
The value of the clinically important differences d	0,15
Estimated differences between groups e	0,0
The size of the main group n_{main}	97
The size of the control group $n_{control}$	97
Estimated share of departures	3
Adjusted main group size	100
Adjusted control group size	100

The final number of patients in each group was adjusted for their possible dropout. Thus, the final number of subjects in each group was 100 patients (200 patients in total).

Test treatment	
 - Treatment with Imupret® oral drops according to the respective Summary of Product characteristics (Imupret® coated tablets or oral drops during acute period for 5 days, afterwards switch to the subacute dosage regimen for further 28 days) - Sparing diet; fractional feeding (5-6 times a day) in small portions with the exception of coarse, spicy, heavily digestible foods - Elimination of factors irritating pharyngeal mucosa (thermal, chemical) 
 - As needed, Paracetamol (Acetaminifen) in a single dose of up to 400 mg not more than 3 times daily or paracetamol in a single dose of up to 500 mg 3-4 times daily (if necessary). - Topical agents such as Benzydamine, Lidocaine as needed (in case of severe sore throat). 	
Reference treatment	
 - Sparing diet; fractional feeding (5-6 times a day) in small portions with the exception of coarse, spicy, heavily digestible foods - Elimination of factors irritating pharyngeal mucosa (thermal, chemical) - As needed, Paracetamol (Acetaminifen) in a single dose of up to 400 mg not more than 3 times daily or paracetamol in a single dose of up to 500 mg 3-4 times daily (if necessary). - Topical agents such as Benzydamine, Lidocaine as needed (in case of severe sore throat). 	
Investigational Medicinal Product	Active (add on) treatment	Imupret® oral drops

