8.3.3 Reference treatment

All patients of the trial will undergo the reference treatment described below. However, only one of the two study groups (study group 1) will receive and add-on treatment with either Imupret® oral solution (see 0 and 8.3.2).

Reference treatment comprises instructions for patient's behavior as well as possible medical treatment when needed:

- Sparing diet with fractional feeding (5-6 times a day) in only small portions explicitly excluding coarse, spicy, or heavily digestible food
- At the discretion of the investigator, elimination of all factors irritating pharyngeal mucosa (e.g. thermal, chemical influence etc.)

At the discretion of the investigator, Paracetamol as single doses up to 500 mg – not more than 3-4 times daily

- At the discretion of the investigator, topical treatment like benzydamine, lidocaine (in case of severe sore throat)
- At the discretion of the investigator, antibiotic treatment in case it is indicated with e.g. amoxicillin clavulanate, cephalosporins (in case of prescription of antibiotics patients will be evaluated separately)

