Checks for general well-being (AE-checks), checks of restrictions and medication will be performed.

The investigator will estimate indicators for prescription of antibiotics and will decide whether a patient will remain on the study treatment or not. If an antibiotic agent is prescribed, details will be documented and the patient will be instructed about the mode of administration. Intake of

antibiotic drug will be documented in the CRF. Patients with intake of antibiotics will be evaluated separately. At the discretion of the investigator the patient may be advised not to take IMP anymore. If so, this will be documented as well.

Self-assessment of the patient's throat pain by him/herself and (or) his/her parent(s) using a visual analogue scale (VAS) is performed afterwards. Moreover, forms for VAS assessment will be handed over to the patient. The patient will have to assess his/her sore throat every study day until visit 4 on study day 10±1.

10.3 Interim evaluation of treatment efficacy- Visit 3

Visit 3 (V3) will be performed on day 5 ±1 by a telephone call.

Intermediate evaluation of the effectiveness of treatment (day 5-day ±1) via telephone (or visit if necessary); patients self-assessment (VAS; 0-10)

10.4 Treatment efficacy, end of Reference treatment - Visit 4

At visit 4 (V4) on day 10 ±1 the status of the disease will be again evaluated.

A physical examination of vital signs (blood pressure, pulse rate, body temperature (axillar)) will be performed. All physical examinations done at V1 including skin and visible mucosa, palpation of abdomen and lymph nodes, oropharyngoscopy will be repeated to assess the status of the tonsillitis.

Again, objective symptoms included in the "Local Tonsillitis Manifestation Scale".

Checks for general well-being (AE-checks), checks of restrictions and medication will be performed.

Self-assessment of the patient's throat pain by him/herself and (or) his/her parent(s) using a visual analogue scale (VAS; 0-10 points) is performed. Forms of VAS assessment will be collected from the patient.

10.5 Treatment efficacy, end of treatment - Visit 5

Visit 5 (V5) will be performed on day 28 by a telephone call (for both the groups).

Checks for general well-being (AE-checks), checks of restrictions and medication will be performed.

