The FAS consists of all randomized patients with at least one documented application of IMP and with at least one observed post-baseline value.

Per Protocol Set (PPS)

The PPS consists of all patients of the FAS without major protocol deviations. The evaluation of protocol deviations and whether they lead to the exclusion of a patient from the PPS will be performed during data review of the study.

Primary endpoint

Main criterion for evaluation in the trial will be:

- Scores determined by the Local Tonsillitis Manifestations Scale refined by McIsaac's scale. Scores will be dichotomized to decide for two categories (therapy effective/therapy ineffective). Scores will be evaluated by treatment and time point, i.e. per visit
- Need for an antibacterial therapy, i.e. number of patients per treatment.

Secondary endpoints

- Scores/Intensity of each underlying disease symptom assessed by the Local Tonsillitis Manifestations Scale by treatment and time point, i.e. per visit
- Axillary temperature per treatment and measurement time point
- Patient's self-assessments on VAS per treatment and measurement time point
- Self-assessment of the symptoms by the patient.

Safety evaluation

AEs will be evaluated considering frequency and intensity. Furthermore, AEs will be evaluated considering relationship to the IMP, outcome, and seriousness. Both will be described by absolute and relative frequency. Descriptive statistics will be calculated for clinical laboratory parameters determined. Frequencies of values inside and out of normal range (i.e. above and below) will be given where possible.

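### The plan sets antibiotic users apart but names no population for the by-arm comparisons of symptom scores, temperature and VAS; if users are left out, those comparisons are no longer randomised

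*Protocol*

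**What the plan says.** The secondary endpoints in Protocol section 12.2.3 are tabulated by arm and time: "Scores/Intensity of each underlying disease symptom assessed by the Local Tonsillitis Manifestations Scale by treatment and time point, i.e. per visit", then axillary temperature and VAS. The SAP, under Secondary endpoints, has the same list, for example "Patient's self-assessments on VAS per treatment and measurement time point". No analysis population is attached to any of them, and no rule covers values recorded after an antibiotic is started.

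Two other places treat antibiotic users as a group of their own. Section 8.3.3 says "in case of prescription of antibiotics patients will be evaluated separately". Section 10.2, on Visit 2, says "Patients with intake of antibiotics will be evaluated separately". One is triggered by prescription and the other by intake, and neither says what the separate evaluation is.

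The analysis sets (section 12.2.1 and the SAP) do not name antibiotic use as a ground for leaving the full analysis set. Antibiotics are also absent from the withdrawal list in section 8.3.4.

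**The concern.** Whether a child receives an antibiotic is settled after randomisation, at Visit 2, from the child's condition, by an investigator who knows the arm (sections 8.4 and 10.2). It is itself an outcome: the first objective in section 7, part of the success definition in the synopsis, and a main criterion in section 12.2.2. If antibiotic users are taken out of the by-arm tables, each arm loses children according to how they fared. If the arms differ in antibiotic use, they lose different numbers and kinds of children. The remaining groups are not the ones randomisation made comparable, and a table of users alone is selected in the same way.

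Visit 2 is affected as well as later visits, because prescribing is decided on the Visit 2 state. At stake is much of the second objective, regression of symptoms, although the main criterion also draws on the local symptom scale. Section 12.2 and the SAP leave the specifications until the database is closed, so the choice between including and excluding users could be made with open-label results in view.

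**Working it through.** **1. The plan's own figure.** Synopsis Table 1 gives 0.75 for "The observed frequency of the positive effect for the control group" and 0.90 for "Estimated value of the positive effect for the main group", with z = 1.96 and 0.84. Its formula gives (1.96 + 0.84)² / (0 − 0.15)² × [0.75 × 0.25 + 0.90 × 0.10] = 7.84 / 0.0225 × 0.2775 = 96.69, so 97 per arm; 97 / 0.97 = 100. The figures reproduce. They concern the main variable and do not settle this point. They are used here only as a source of failure shares: 1 − 0.75 = 25% and 1 − 0.90 = 10%.

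**2. Assumptions.** The documents give no antibiotic rates. Suppose every planned failure, and nobody else, takes an antibiotic: 25% control, 10% Imupret. Let Visit 2 severity be normal with SD 1 (higher is worse), with control mean 0. An antibiotic is given above one threshold c common to both arms.

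**3. Visit 2 with users removed.**
- Control: c = 0.674.
- Imupret: c − μ = 1.282, so the true shift is μ = 0.674 − 1.282, about −0.607 SD.
- The mean of those left is μ − φ(a)/Φ(a), with a = c − μ.
- Control: −0.3178 / 0.75 = −0.424.
- Imupret: −0.607 − 0.1755 / 0.90 = −0.607 − 0.195 = −0.802.
- Remaining difference: −0.802 + 0.424 = −0.378. The loss is 0.229 SD, with 62% retained.

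**4. Later visits.** If the later score correlates ρ with Visit 2 severity, the loss is ρ × 0.229. It is 0.229 at full tracking and about 0.11 at ρ = 0.5, where −0.61 becomes −0.49. For ρ from 0.3 to 0.7 the remaining difference runs from −0.54 to −0.45 SD.

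**5. Other rates (same model, full tracking).**

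| Antibiotic use, control v Imupret | True shift (SD) | Users removed (SD) | Retained |
|---|---|---|---|
| 12.5% v 5% | −0.495 | −0.368 | 74% |
| 30% v 20% | −0.317 | −0.170 | 54% |
| 40% v 25% | −0.421 | −0.201 | 48% |
| 50% v 35% | −0.385 | −0.157 | 41% |

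**6. No true symptom effect.** If controls are simply prescribed at a lower severity threshold (25% v 10%), the difference among those left is −0.195 − (−0.424) = +0.229 SD against Imupret, or about 0.11 SD at ρ = 0.5. With equal rates and no effect it is 0.

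**7. Size against sampling error.** Of 100 per arm, 75 and 90 remain. The variance after truncation is 1 − aλ − λ², with λ = φ(a)/Φ(a): 0.535 for control and 0.712 for Imupret. The standard error is √(0.535/75 + 0.712/90) = 0.123, so 0.229 is about 1.9 standard errors. At ρ = 0.5 it is about 0.8.

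**8. Against all randomised children with observed scores.** If an antibiotic lowers the later score by b SD, the all-randomised difference is −0.607 + (0.25 − 0.10) × b. For b = 0, 0.5, 1 and 2 this is −0.61, −0.53, −0.46 and −0.31. Removal at ρ = 0.5 gives −0.49. Removal therefore understates Imupret's advantage relative to this comparison when b is below 0.114 / 0.15 = 0.76 SD, and overstates it above that.

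**The case against.** A reader might infer that the plan removes antibiotic users from these tables. It does not say so. A separate evaluation may mean removal, a subgroup table or an added analysis. The full analysis set does not exclude these children for taking antibiotics, section 8.3.4 does not require their withdrawal, and section 8.3.3 lists antibiotics within the reference treatment. Removal is the natural reading, but not the only one. What stands is that the passages do not fit together and no rule decides between them.

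A reader might also infer a sure bias against Imupret. That needs three conditions: prescribing follows severity, rates differ, and the target is the effect without antibiotics. If unblinded prescribers treated more controls regardless of severity, removal would cause no bias, and step 8 shows the direction reversing against observed scores.

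The figures are close to a worst case. Failure in the synopsis also covers any symptom left above 1 point, so 25% v 10% probably overstates the antibiotic use implied by the plan, and sorting strictly by severity is an extreme.

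Finally, the trial calls itself exploratory and these are secondary endpoints with no named test. That lowers the stakes. It does not make a comparison selected on outcome informative about treatment.

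**Conclusion.** The point holds as a gap with a conditional consequence. The population and the handling of data after antibiotic start are undefined for the local symptom scores, temperature and VAS, and two passages pull against the analysis sets. If users are excluded, the by-arm comparison from Visit 2 onward is not protected by randomisation.

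Under the stated model the loss relative to the effect without antibiotics is at most 0.23 SD at 25% v 10% (0.61 to 0.38 SD), about 0.11 SD at correlation 0.5, and 0.13 SD if half the failures take antibiotics with full tracking. These are illustrations, not expected values. The documents do not support a fixed direction or a fixed size. The change is worth making; confidence is medium because the meaning of the separate evaluation is open.

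**What to change.** Reconcile sections 8.3.3 and 10.2 with sections 12.2.1 and 12.2.3 and the SAP. Before the data are seen, state in section 12.2.3 and the SAP that:

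1. Every between-arm comparison of local symptom scores, temperature and VAS uses all randomised children in their assigned arm, with observed scores, whether or not they took an antibiotic.
2. The antibiotic-free and antibiotic-user tables are descriptive, with no between-arm test, and membership is defined by one trigger (prescription or intake).
3. The all-randomised comparison includes any effect of antibiotics, so it may dilute a benefit if controls receive more of them. Antibiotic use by arm is shown beside it.

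Ranking antibiotic users below all other children may be shown as a labelled sensitivity analysis only. It turns each symptom comparison partly into a test of open-label prescribing. Simulating no symptom effect, 25% v 10% use, 100 per arm and a two-sided 0.05 rank test, false significance in favour of Imupret was about 25% at correlation 0.5, and 45% to 48% when prescribing was unrelated to severity.

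The cost is wording in two documents. Antibiotic intake is already recorded in the CRF (section 10.2). The price in interpretation is the dilution named in item 3.

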5 TRIAL SYNOPSIS

Trial code	ATi-2
Title of Trial	A Protocol of a Multicenter, Randomized, Open-Label, Comparative Study of Therapeutic Efficacy, Safety and Tolerability of Imupret application in the therapeutic concept of delayed prescription of antibiotics in children, aged 6-12 with severe acute tonsillitis.
Working title	Imupret in tonsillitis
Trial Design	open-label, exploratory, comparative, multicentre, randomized, prospective, parallel-group study.
Clinical phase	IV
Inclusion diagnosis	Acute tonsillitis
Trial objectives	
Assessment of the influence of Imupret (drops) prescriptions in the therapeutic concept of delayed prescription of antibiotics to:
 
 • need for antibiotics • regression of the tonsillitis symptoms • duration of antipyretics administration
Number of patients	approximately N=200 (1:1 ratio active treatment: reference)
Specialization of investigator	Head of Department of Otorhinolaryngology Head & Neck Surgery
Time schedule	Planned FPI (First patient in): approximately February 2019 Planned LPO (Last patient out): approximately December 2019
Efficacy endpoints	
The main criterion (main variable):
 
 - decrease in the severity of each symptom (complaint) that is part of the Mclsaac scale of tonsillitis manifestations, up to 1 point or less. This variable is dichotomous, with the categories "treatment effective" and "treatment not effective": - Treatment is effective - reducing the severity of each symptom (complaint) that is part of the Local Tonsillitis Manifestation Scale (0-15), of tonsillitis manifestations, up to 1 point or less in the evaluation stages. Absence of indications for prescribing antibacterial therapy - Treatment is not effective - the condition given for the category "therapy is effective" is not met.
Secondary end-points	
Secondary variables:
 
 - a decrease in the severity of the symptoms of the underlying disease, at the 2- nd, 3 -rd and 4- th visits compared to the 1- st visit. - decrease in the total score (the sum of scores for each symptom) according to the scale of local manifestations of tonsillitis at the 2-nd, 3-rd and 4-th visits in comparison with the 1-st visit. - a decrease in temperature in the armpit at the 2-nd and 3-rd visits compared to the 1-st visit. - a patient's self-assessment of the quality of life (every day). - Duration of NSAID administration. -Therapy compliance

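### No baseline adjustment is specified for symptom scores, VAS or temperature although visit 1 values are collected; naming it before database closure would gain precision at little cost

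*Protocol*

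**What the plan says.** The continuous endpoints appear in two forms.

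- **By arm and visit.** Protocol section 12.2.3 lists symptom scores "assessed by the Local Tonsillitis Manifestations Scale by treatment and time point, i.e. per visit", with temperature and VAS laid out the same way. The SAP repeats the list, for example "Patient's self-assessments on VAS per treatment and measurement time point". Section 12.2.2 says of the local-scale scores behind the main criterion: "Scores will be evaluated by treatment and time point, i.e. per visit".
- **As decreases from visit 1.** The synopsis lists a "decrease in the total score (the sum of scores for each symptom"), and likewise decreases in symptom severity and in axillary temperature.

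Visit 1 values are collected. Section 8.5 puts the local scale and VAS at visit 1, and section 10.1 adds axillary temperature and a throat-pain VAS.

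Neither document mentions a covariate, ANCOVA or a repeated-measures model. Section 12.2 and the SAP plan descriptive summaries, make inferential statistics optional and open to being led by the data, and defer the analysis specifications until the database is closed. They also promise technical details before analysis, but that is compatible with setting them after closure.

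**The concern.** A visit value taken alone ignores where the child started. A raw decrease subtracts the whole starting value and so over-corrects whenever the regression of follow-up on baseline has a slope below 1. Adjusting for the visit 1 value uses the same data more efficiently. It also removes the effect of a chance difference in entry severity between arms, which matters somewhat because section 8.4 describes no stratification.

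The trial is open-label, and the model is to be chosen after closure. Visit value, decrease and adjusted difference can give different answers from one data set, and nothing in the plan says which is to be reported.

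**Working it through.** **The plan's own figure.** The only sample size is in the synopsis, for the binary main variable. Its inputs are "the two-way probability of making a type 1 error is 0.05" (z = 1.96), 80% power (z = 0.84), "The observed frequency of the positive effect for the control group" = 0.75, "Estimated value of the positive effect for the main group" = 0.90, d = 0.15 and e = 0.0 as listed in Table 1.

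n = (1.96 + 0.84)² / (0 − 0.15)² × (0.75 × 0.25 + 0.90 × 0.10) = 7.84 / 0.0225 × 0.2775 = 96.69, so 97 per arm, and 100 after dropout. It reproduces. It is not affected by this point, and no power is stated for any continuous endpoint.

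**Assumptions.** The documents give no SD, effect size or correlation for the continuous endpoints. I take r, the within-arm correlation of visit 1 with follow-up, from 0.2 to 0.7, and measure effects in follow-up SD units.

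**Variance of the treatment difference**, relative to the follow-up value alone:

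- per-visit value: 1
- raw decrease, equal SDs: 2(1 − r)
- adjusted for visit 1: 1 − r²
- adjusted against decrease: (1 − r²) / [2(1 − r)] = (1 + r)/2

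Detectable difference at 97 per arm, 80% power, two-sided 0.05: 2.80 × √(2/97) = 0.402 SD for the per-visit value, multiplied by the square root of the relative variance for the other two.

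| r | Variance, decrease | Variance, adjusted | Cut against visit value | Cut against decrease | Detectable: visit / decrease / adjusted (SD) |
|---|---|---|---|---|---|
| 0.2 | 1.60 | 0.96 | 4% | 40% | 0.402 / 0.509 / 0.394 |
| 0.3 | 1.40 | 0.91 | 9% | 35% | 0.402 / 0.476 / 0.384 |
| 0.5 | 1.00 | 0.75 | 25% | 25% | 0.402 / 0.402 / 0.348 |
| 0.7 | 0.60 | 0.51 | 49% | 15% | 0.402 / 0.312 / 0.287 |

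The cut against the visit value is r²; at r = 0.7 it is 1 − 0.51 = 0.49. At r = 0.5 the gain equals 97 / 0.75 = 129 patients per arm instead of 97. Below r = 0.5 the raw decrease is less precise than ignoring baseline.

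**Unequal SDs.** Let k be the visit 1 SD divided by the follow-up SD. The decrease has relative variance 1 + k² − 2rk = (1 − r²) + (k − r)². In the large-sample linear model, adjustment is therefore never less precise than the decrease, but the gain, (k − r)², may be larger or smaller than in the table. The factor 1 − r² does not need equal SDs.

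**Chance imbalance.** With 100 per arm, the visit 1 mean difference has SE √(2/100) = 0.141 SD, so 95% of trials fall within ±1.96 × 0.141 = ±0.277 SD. With equal SDs a fraction r enters the visit-value estimate, and −(1 − r) enters the change (follow-up minus visit 1). For an imbalance of 0.277 SD the shifts are 0.06 and −0.22 at r = 0.2, 0.14 and −0.14 at r = 0.5, and 0.19 and −0.08 at r = 0.7.

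**The case against.** The strongest reply is that the documents contain no unadjusted analysis to criticise. A reader might infer that the plan commits to comparing raw values or raw decreases. It does not: listing a measure by treatment and visit is a tabulation layout, and no test or model is named. Nor does defining an endpoint as a decrease exclude adjustment, since regressing the change on arm and visit 1 gives the same treatment estimate as regressing the follow-up value on them. This stands; the defect is an omission within a wider deferral of the analysis specifications.

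A reader might also infer that chance imbalance carries over in full, or that unadjusted results would be biased. Neither holds. Only the fractions shown above carry over, and randomisation keeps both unadjusted estimators unbiased.

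A third tempting inference is that the responder rule depends strongly on entry severity. The documents give no data on this, and response also requires that there be no indication for antibiotics.

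The gain may also be small. Entry requires severe tonsillitis with McIsaac 4–5, which may narrow the visit 1 spread, and scores may be near zero by day 10. At r = 0.2 the gain over the per-visit value is only 4%. That stands, and it is why a range is given.

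What survives is that visit 1 values are collected, no adjustment is specified, and both forms the plan does state are in general less precise.

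**Conclusion.** The point holds as an omission of modest consequence. For r between 0.2 and 0.7, adjusting for visit 1 would cut variance by 4% to 49% against the per-visit value and, with equal SDs, by 40% to 15% against the raw decrease. No exact loss can be stated because r and the SDs are not in the documents.

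These continuous endpoints are secondary in a trial described as exploratory, and no powered claim rests on them. What is lost is precision, and what is left open is the choice among three estimators after closure. No stated figure is wrong.

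**What to change.** Before database closure:

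1. **Reconcile the measures**, so that covariate and outcome match. The local scale has five items (0–15) in section 8.5 but seven in section 10.6, which would run to 7 × 3 = 21. The visit 1 VAS is throat pain alone in section 10.1 but four items in section 10.6.
2. **Name the model in the SAP.** Compare the local-scale total and axillary temperature at visits 2 and 4, and throat-pain VAS over time, by ANCOVA or a repeated-measures model with arm and the visit 1 value of the same measure. Report the adjusted difference with a 95% CI. Include visit 3 for the scale and temperature only where an in-person visit occurs, because it is normally a telephone call.
3. **Keep single symptoms descriptive.** A linear model for each 0–3 item, with a likely floor, is debatable.
4. **Responder criterion, optional.** A visit 1-adjusted risk difference may be shown beside the crude one as supportive. At the planned rates, 97 × 0.25 + 97 × 0.10, or about 34 non-responders, are expected, enough for arm and one covariate.

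The cost is SAP wording, the reconciliation and a little programming. No new data are needed.
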